6.2.9 Visit X (8 weeks)

This visit is only performed if bone healing was not sufficient at Visit 3 (6 weeks), defined as mRUS < 11 in any fractured bone.

- Assessment for any adverse events (AEs) since the previous visit, including documentation and reporting as applicable
- Radiographs
- Clinical examination and outcome assessments as described in Section 7
- Source data verification and entry into the eCRF
- Scheduling of the next visit:
 - If bone healing is not sufficient, defined as mRUS < 11 in any fractured bone, a follow-up visit will be scheduled at 10 weeks postoperatively.
 - If bone healing is sufficient (mRUS ≥ 11 in all fractured bones), the next visit will be scheduled at 3 months postoperatively.

6.2.10 Visit Y (10 weeks)

This visit is only performed if bone healing was not sufficient at Visit X (8 weeks), defined as mRUS < 11 in any fractured bone.

- Assessment for any adverse events (AEs) since the previous visit, including documentation and reporting as applicable
- Radiographs
- Clinical examination and outcome assessments as described in Section 7
- Source data verification and entry into the eCRF
- Scheduling of the next visit

6.2.11 Visit 6 (12 weeks)

- Assessment for any adverse events (AEs) since the previous visit, including documentation and reporting as applicable

- Radiographs
- Clinical examination and outcome assessments as described in Section 7
- Test of Motor Proficiency administered by an occupational therapist
- Source data verification and entry into the eCRF
- Scheduling of the next visit

6.2.12 Visit 7 (24 weeks \pm 2 weeks)

- Assessment for any adverse events (AEs) since the previous visit, including documentation and reporting as applicable
- Radiographs
- Clinical examination and outcome assessments as described in Section 7
- Test of Motor Proficiency administered by an occupational therapist
- Disclosure of treatment allocation (unblinding)
- For the titanium elastic nail (TEN) group, implant removal surgery will be planned in accordance with standard of care
- Source data verification and entry into the eCRF
- Scheduling of the next visit

6.2.13 Visit 8 (52 weeks \pm 4 weeks)

- Assessment for any adverse events (AEs) since the previous visit, including documentation and reporting as applicable
- Radiographs
- Clinical examination and outcome assessments as described in Section 7
- Source data verification and entry into the eCRF
- Scheduling of the next visit

6.2.14 TEN removal surgery

Implant removal in the titanium elastic nail (TEN) group will be performed according to standard of care, 6–12 months after implantation.

6.2.15 Visit 9 (104 weeks \pm 4 weeks)

- Assessment for any adverse events (AEs) since the previous visit, including documentation and reporting as applicable
- Radiographs
- Clinical examination and outcome assessments as described in Section 7
- Source data verification and entry into the eCRF
- End of study participation

6.2.16 Unscheduled visits

Unscheduled visits may occur at any time during the study if a medical concern arises or if deemed necessary by the investigator for patient care.

All unscheduled visits or unplanned patient contacts related to the injury, treatment, or study device will be documented in the patient's medical record as part of standard care.

For study purposes, unscheduled visits will be captured in a dedicated Unscheduled Visit form in the eCRF, as described in the corresponding SOP. The form will document the date, reason for contact,

and whether the contact resulted in an adverse event, additional treatment, or a change to the follow-up schedule.

Treatment-related adverse events will be recorded and reported in accordance with Section 11 and the corresponding SOP.

Data obtained during unscheduled visits will be reviewed and, where relevant, incorporated into the study database at the next scheduled study visit.

6.2.17 Premature study termination

A participant's involvement in the study may end prematurely (discontinuation of study participation) and/or the participant may discontinue the allocated treatment while remaining in study follow-up.

Reasons may include, but are not limited to:

- Withdrawal of informed consent (for study participation and/or use of data)
- Protocol deviation/violation with potential impact on participant safety or data integrity
- Refracture and/or reoperation (e.g., infection, implant-related complication)
- Investigator's decision (e.g., noncompliance with study procedures, safety concerns)
- Sponsor's decision (e.g., early study termination, safety signal, or regulatory request)
- Lost to follow-up
- Death

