6.1.4.6 Informed consent

A more detailed description of the informed consent process is provided in Section 10.

- All participants for whom written informed consent has been obtained will be assigned a unique trial participant number.
- The date of informed consent and recruitment details will be recorded in the study database.
- Participants who commence any study treatment are considered enrolled.
- All enrolled participants will be followed within the study unless participation is terminated prematurely for reasons specified in Section 6.2.17.

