8.3.2 Analysis populations

In non-inferiority trials, intention-to-treat (ITT) analyses may be biased toward non-inferiority due to treatment cross-over and non-adherence. We intend to analyze both the per-protocol (PP) and ITT populations. The primary non-inferiority analysis will be performed in the PP population. A supportive analysis will be performed in the ITT population. Non-inferiority will be considered robust if conclusions are consistent in both PP and ITT analyses. We suspect very few cases will cross over. We suspect to find similar results in both groups and a discrepancy would warrant close examination of the results.

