8.3.4 Intention-to-Treat (ITT) population

Intention-to-Treat (ITT) population will include all randomized participants analyzed according to their randomized treatment allocation, regardless of the treatment actually received, protocol deviations, or subsequent withdrawal from the assigned intervention. Participants will contribute all available follow-up data collected until withdrawal of consent or study end. The ITT population will be used for supportive analyses of the primary endpoint and for key secondary outcomes, complementing the primary Per-Protocol analysis in this non-inferiority trial.

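### Section 6.2.17 permits a child's follow-up to end for a protocol deviation or non-compliance, which conflicts with the ITT definition and can weaken the PP/ITT consistency check

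*Protocol*

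**What the plan says.** Section 6.2.17 describes two outcomes under one heading. A child's involvement in the study may end early, and/or "the participant may discontinue the allocated treatment while remaining in study follow-up". A single list of possible reasons follows and does not say which reason leads to which outcome. Two entries matter here: "Protocol deviation/violation with potential impact on participant safety or data integrity", and an investigator's decision, for which the examples are "noncompliance with study procedures, safety concerns".

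Section 6.1.4.6 says that all enrolled children are followed "unless participation is terminated prematurely for reasons specified in Section 6.2.17". Section 6.2.17.1 offers one early termination visit, if feasible and agreed. Under 6.2.17.2 and 8.3.10, a child with no film showing healing is right-censored at the last evaluable film.

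Section 8.3.4 defines ITT by randomised allocation, irrespective of deviations, and adds: "Participants will contribute all available follow-up data collected until withdrawal of consent or study end". Section 8.3.2 makes PP the primary analysis and ITT supportive, with the criterion: "Non-inferiority will be considered robust if conclusions are consistent in both PP and ITT analyses".

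**The concern.** In a non-inferiority trial with PP as the primary set, the ITT analysis shows whether the result survives when the children PP leaves out are put back. That works only if those children are still observed. Sections 6.2.17 and 6.1.4.6 together allow an investigator to end follow-up for the kind of reason that also removes a child from PP. Section 8.3.4 assumes that this does not happen: a child removed for a deviation has not withdrawn consent, and the study has not ended, yet scheduled data collection stops.

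If the option is used in the first weeks, ITT still counts the child but learns almost nothing from that child. Agreement between PP and ITT then partly reflects missing films rather than similar healing. A sensitivity analysis in the SAP can vary assumptions about those children but cannot recover films that were never taken.

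**Working it through.** **1. The rules side by side.**
- 6.2.17: deviation or non-compliance may end participation; the wording is permissive.
- 6.1.4.6: the 6.2.17 reasons are the stated exception to follow-up.
- 8.3.4: deviations do not matter for ITT; data run to consent withdrawal or study end.

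The first two permit what the third excludes. They are compatible only if the option is never used for these two reasons.

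**2. Which children.** Section 6.2.17 covers deviations that may affect safety or data integrity. PP (8.3.3, 8.3.3.1) excludes major deviations that affect the healing assessment, including a non-allocated device, no fixation, and a cast duration off by more than 7 days. The two sets are not defined as the same, but they can overlap. Device and cast deviations arise at surgery or around the planned cast periods of 2 weeks (TEN) and 4 weeks (BIN).

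**3. Planning values.** One-sided alpha 0.025, power 90%, SD 3 weeks, margin 3 weeks (8.2): n = 2 × (1.960 + 1.282)² × 3²/3² = 21.01, so 22 per group; 22/0.90 = 24.4, so 25. Both match 8.2.7. The point concerns follow-up, so no sample size changes.

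**4. What an early-censored child contributes.** Take a Weibull distribution with mean 8 and SD 3 weeks (8.2.2). Shape k solves √(Γ(1+2/k)/Γ(1+1/k)² − 1) = 3/8, giving k = 2.90; scale = 8/Γ(1+1/k) = 8.97. Then F(t) = 1 − exp(−(t/8.97)^2.90), so F(2) = 1.3% and F(4) = 9.2%. A child censored at week 4 shows only that healing had not occurred at a time when about 91% would be unhealed anyway.

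**5. Effect on the estimate.** Simulation with an interval-censored Weibull model, 30 per arm, films at 2, 4, 6, 8, 10, 12, 24, 52 and 104 weeks, no true difference apart from the deviators, 300 trials per row. Assumptions not in the documents: deviators only in the BIN arm, their share, their delay, and filming that stops at week 4. Entries are the mean BIN minus TEN difference in median time (weeks). The last column is the percentage of trials with non-inferiority concluded, for the three analyses in the same order.

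| Share, delay | ITT, films continued | ITT, films stopped | PP | Gap to PP: continued / stopped | Non-inferior (%) |
|---|---|---|---|---|---|
| 5%, 4 wk | 0.33 | 0.12 | 0.10 | 0.23 / 0.02 | 92 / 94 / 95 |
| 10%, 4 wk | 0.40 | 0.04 | 0.00 | 0.40 / 0.04 | 89 / 96 / 97 |
| 20%, 4 wk | 0.79 | 0.06 | −0.01 | 0.80 / 0.07 | 75 / 94 / 95 |
| 10%, 8 wk | 0.66 | 0.00 | −0.04 | 0.70 / 0.04 | 80 / 98 / 98 |
| 20%, 8 wk | 1.46 | 0.09 | 0.02 | 1.44 / 0.07 | 40 / 92 / 93 |

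The three analyses in a row use the same simulated trials, so the gaps are more precise than the levels.

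**6. Effect on the conclusion.** Section 8.3.2 compares conclusions, not estimates. With 3 deviators per arm (10%), the BIN deviators healing 6 weeks late, and 400 trials, the mean estimates are 0.58 (ITT, films continued), 0.06 (ITT, films stopped) and 0.03 (PP). The ITT and PP verdicts differ in about 9% of trials with films continued and about 1% with films stopped. With one deviator per arm they differ in no more than about 3% even with complete films.

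**The case against.** A reader might infer that deviating children stop being filmed and that ITT therefore cannot check PP. The documents do not support that.
- Section 6.2.17 says participation may end and offers remaining in follow-up as an alternative. Treatment is a package of nail and cast (6.3), so a departure from the package can fall under that alternative.
- Only deviations bearing on safety or data integrity are listed, and no section says that a PP exclusion triggers removal.
- Section 8.3.4 still counts every randomised child, and films taken before discontinuation are kept.
- The early termination visit may add a film. Section 9.1 lists standard-care films for TEN at 2 and 6 weeks and before removal, and 12.1.1 seeks consent to image access until study completion.
- Section 8.3.2 expects very few cross-overs, and with few deviators the two verdicts would seldom differ anyway.
- Section 6.2.17.2 leaves sensitivity analyses for informative missingness to the SAP.

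All of this limits the point, and most of it stands. It does not remove the conflict. The list never says that deviation leads only to the stay-in-follow-up outcome. The termination visit is single and conditional and, if it falls before healing, only moves the censoring date. The protocol does not say that later clinical films of a terminated child would be scored. The expectation of few cross-overs does not cover cast-duration deviations or missed procedures.

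**Conclusion.** The point holds as a conflict between a permission and a definition. Sections 6.2.17 and 6.1.4.6 allow follow-up to end for deviation or non-compliance, whereas 8.3.4 assumes that it continues. Where the option is used before healing, ITT tends to reproduce PP, and the agreement criterion in 8.3.2 becomes less informative.

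The size depends on how many children deviate, how late they heal and how often the option is used, none of which the documents give. Under the assumed 5-20% deviators in the BIN arm with a 4-8 week delay, the ITT-PP gap is 0.02-0.07 weeks if filming stops and about 0.2-1.5 weeks if it continues, that is up to about half the 3-week margin (1.44/3 = 48%). At the low end, the conclusion would rarely change.

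The point does not extend to refracture or reoperation. For healing-related reoperation, 8.3.8 censors at the last earlier film whether or not the child stays, and it provides its own sensitivity analysis.

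**What to change.** In 6.2.17, separate the two outcomes for these reasons. State that a protocol deviation/violation or non-compliance alone does not end study follow-up. It is recorded and used to define the PP set; the child stays on the scheduled radiographic follow-up and contributes to ITT under 8.3.4 unless consent is withdrawn. The investigator-decision entry needs splitting, because it puts non-compliance and safety concerns together and only the former should change.

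Leave the other reasons as they are: sponsor or regulatory decision, safety concerns, refracture/reoperation, loss to follow-up and death. Align the exception in 6.1.4.6. The change concerns data collection only and leaves treatment decisions untouched.

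The cost is protocol wording, handled as an amendment, plus the effort of keeping non-compliant families attending. The visits and films are already in the schedule, and the sample size does not change.

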6.2.17.1 Procedures and documentation

For all premature terminations/discontinuations, the Investigator will document the primary reason and relevant details in the eCRF (dropout/discontinuation form). Where appropriate, the case will be discussed with the Sponsor. If feasible, and if the participant and parents agree, an early termination visit will be performed to capture key outcome assessments and to collect information on adverse events/serious adverse events up to the time of discontinuation.

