11.4 Follow-up of adverse events

Each AE will be followed up until resolved with or without persistent damage or until the end of the patient's study participation.

All patients experiencing an AE must be monitored until the symptoms subside and any clinically relevant changes in laboratory values have returned to baseline, or until there is a satisfactory explanation for the changes observed. The results of any additional diagnostic measure (not included in the CIP) that are obtained because of the occurrence of an AE or SAE should be attached to the eCRF highlighting the date on which these measurements were taken.

For any deaths occurring during the study, a postmortem report must be supplied by the investigator to the sponsor, whenever possible.

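### The protocol lets refracture or reoperation end a child's study participation, so later safety and functional data can be lost because of the event itself

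*Protocol*

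**What the plan says.** Section 6.2.17, headed premature study termination, opens with two different consequences: "A participant's involvement in the study may end prematurely (discontinuation of study participation) and/or the participant may discontinue the allocated treatment while remaining in study", meaning in the second case that observation continues. A single, non-exhaustive list of reasons then serves both. It holds consent withdrawal, loss to follow-up, death, protocol deviation, investigator and sponsor decisions, and "Refracture and/or reoperation (e.g., infection, implant-related complication". No reason is assigned to either consequence.

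Four other places depend on that list or on the end of participation:

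- Section 6.1.4.6: "All enrolled participants will be followed within the study unless participation is terminated prematurely for reasons specified in Section 6.2.17".
- Section 6.2.17.1: an early termination visit takes place only if feasible and if the family agrees. One of its purposes is "to collect information on adverse events/serious adverse events up to the time of discontinuation".
- Section 11.4, first sentence: "Each AE will be followed up until resolved with or without persistent damage or until the end of the patient's study participation".
- Section 11.4, second paragraph: "All patients experiencing an AE must be monitored until the symptoms subside". No limit tied to participation is given.

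On the analysis side, section 8.3.4 says of the ITT population: "Participants will contribute all available follow-up data collected until withdrawal of consent or study end".

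**The concern.** Refracture rate, surgical complications and implant-related complications are secondary objectives (5.2). Refracture, deep infection and reoperation are reviewed at the interim safety look (19.1). These are the children whose later course matters most for comparing the two implants, and the text allows them to be closed out for that very reason.

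Exit would then depend on a bad outcome. Any later refracture, further reoperation or late infection, and the range of motion, grip strength, pain and EQ-5D-Y results at the remaining visits, would be missing for children who are not a random subset. If events are more frequent in one arm, the 1- and 2-year functional summary of that arm would rest on its better outcomes. A later analysis plan cannot recover data that were never collected, so the matter belongs in the protocol.

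**Working it through.** **1. Does the text permit exit?** Read in order:

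| Section | Rule | Effect after refracture or reoperation |
|---|---|---|
| 6.2.17 | One list, two consequences | Either route is open |
| 6.1.4.6 | All enrolled children followed, except for 6.2.17 reasons | Exit complies with the protocol |
| 6.2.17.1 | Adverse events collected to discontinuation, at a conditional visit | Index event recorded; no later collection |
| 11.4, first sentence | Follow-up to resolution or end of participation | Can stop before resolution |
| 11.4, second paragraph | Monitoring until symptoms subside | Conflicts with the line above; covers the existing event, not new ones |

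Exit is therefore permitted and not required.

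**2. Does it fit the rest of the protocol?** Section 3 commits the site to complete documentation for all enrolled participants, meaning all scheduled visits. The Definitions equate the follow-up population with the enrolled population. Section 8.3.4 envisages ITT data up to consent withdrawal or study end. Section 19 keeps enrolled children in follow-up to the final visit, where feasible, even if the whole study stops early. Exit for refracture is in tension with each of these.

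**3. Is exit needed for the primary endpoint?** No. Sections 6.2.17.2 and 8.3.8 censor time to healing at the last evaluable radiograph before the event. That is a rule about one endpoint and works equally well with the child still under observation.

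**4. How many children?** The 5% allowance comes from the sample size section, whose figures reproduce: 2 × (1.960 + 1.282)² × 3² / 3² = 21.0, rounded up to 22 per group; 22 / 0.90 = 24.4, rounded up to 25. Planned enrolment is 30 per group, 60 in total (8.2.7).

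- Intercurrent events at about 5% (8.2.6): 0.05 × 60 = 3 children.
- Anticipated reoperation for any reason, 0.1 to 0.5% (7.2.6.4): 0.001 × 60 = 0.06 to 0.005 × 60 = 0.3 children.
- Refracture: section 7.2.6 gives no expected rate.

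**5. How much is lost per child?** Planned follow-up is 104 weeks, about 24 months. As an illustration, exit at month 4 loses 24 − 4 = 20 months and the 6-month, 1-year and 2-year visits. The satisfaction questionnaire is given only at 2 years (7.2.14), so it is lost as well.

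**6. What could this do to a mean?** Suppose affected children score d worse on average than the others (d is not given in the protocol). Dropping k of 30 children in an arm overstates that arm's mean by (k/30) × d. If all three affected children are in one arm, the between-arm difference is off by 3/30 × d = 0.10d. With a 2:1 split and the same d in both arms, it is off by (2/30 − 1/30) × d = 0.033d. The error hides a disadvantage of the arm with more events.

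**The case against.** The strongest reply is that section 6.2.17 explicitly offers the route of stopping treatment and staying in follow-up, and that its reasons only may lead to exit. This stands: nobody can say the protocol requires these children to leave. What it does not supply is any statement that refracture or reoperation leads to that route.

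A reader might infer that the allocated treatment is over once the nail is in, so that only exit remains. The documents do not support that. Treatment is a package of nail plus 4 or 2 weeks of casting (6.3), and implant removal for deep infection is a named reoperation (8.3.8).

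A reader might also infer that follow-up of the event itself simply stops. The second paragraph of 11.4 says otherwise, so the accurate description is that 11.4 is inconsistent with itself. In addition, consent covers access to hospital records until study completion (12.1.1). That is a permission, not a duty to collect, and it does not replace study examinations or questionnaires.

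Calling 8.3.4 contradicted goes too far, since it refers to data that are available and collected. Nor is the 25% refracture rule in 19.1 defeated: the index refracture is recorded before any exit and still counts. Only a first refracture in a child already closed out for another reason could be missed. Reoperation and infection are reviewed at the safety look but are not pause criteria. The two criteria are refracture above 25% and mean BIN healing time above 12 weeks.

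**Conclusion.** The concern holds as a gap in the wording: the protocol permits, without requiring, a child to leave follow-up because of refracture or reoperation, and 11.4 gives two different end points for following the event. The index event is kept; later safety events and function to week 104 can be lost in an outcome-dependent way.

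The likely size is small. It is about 3 of 60 children if the whole 5% intercurrent-event allowance is taken, and less than one child on the anticipated reoperation risk alone. The 5% figure allows for events affecting the primary endpoint and is not a forecast of exits; with no expected refracture rate given, it is not an upper bound either. One could point to 7 of 30 BIN children (23.3%) refracturing without the 25% limit being exceeded, since 8 of 30 is the first count above it. That is only a ceiling, and nothing in the protocol suggests such a rate.

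Any bias in the functional comparison rests on two conditions: that the site uses the exit route, and that events are unequal between arms. The primary endpoint is unaffected by exit for these events. This is a should-fix, best settled before enrolment because data not collected after exit may not be recoverable.

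**What to change.** Split section 6.2.17 into two lists.

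1. Reasons that end study participation: withdrawal of consent, loss to follow-up, death, and a documented sponsor or investigator decision. Word the sponsor entry to agree with section 19, under which enrolled children continue follow-up where feasible after early termination.
2. Events that may censor the primary endpoint but do not by themselves end participation: refracture, reoperation for any cause, and protocol deviation. After these the child keeps the scheduled visits through week 104 unless consent is withdrawn.

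Then align 6.1.4.6, so that only the first list is the exception to follow-up; 6.2.17.1, so that the early termination visit applies only to the first list; and 11.4, so that its two paragraphs give one end point. Do not extend follow-up beyond the planned last visit. Nothing here concerns how these events are treated.

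The cost is a protocol amendment of wording. The visits are already scheduled for these children, so no new procedures are needed.
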